Unless stated otherwise, missing data will not be imputed. However, if there are dates missing for AEs or medications, some intermediate steps may be taken for the determination of being treatment emergent or not. Sections below address such procedures for the handling of those dates in the relevant analyses:

Missing or Partial AE or Medication start or stop date:

For missing or partial start-dates:

- 1. If the onset date is unknown, then the date will not be imputed and will be assigned a missing value.
- 2. If the month and day are unknown, then:
 - a. If the year matches the year of the first dose date, then impute the month and day of the first dose date.
 - b. Otherwise, assign as missing.
- 3. If the day of the month is unknown, then:
 - a. If the month and year match the month and year of the first dose date, then impute the day of the first dose date.
 - b. Otherwise, assign as missing.

For partial end-dates:

- 1. If the year is unknown, then the date will not be imputed and will be assigned a missing value.
- 2. If the month is unknown, then assign as missing.
- 3. If the day is unknown, then assign the last day of the month.

Missing Pharmacokinetic (PK) Data:

Missing FT-2102 concentration data in a given profile will not be imputed. Missing samples will be reported as no sample ("NS") and excluded from analysis. The affected

profile(s) will be evaluated whether sufficient FT-2102 concentrations are available to calculate any of the planned PK parameters.

FT-2102 concentrations below the lower limit of quantitation (LLOQ) will be indicated by BLQ in the listings and will be treated as follows:

• For predose samples prior to the FT-2102 administration: Concentrations that are BLQ or missing will be assigned a numerical value of zero for the calculation of AUC. Any anomalous concentration values observed at predose will be included in the computation of AUC. If the predose concentration is greater than 5% of C_{max}, the data will be evaluated on a case-by-case basis to determine if exclusion of the affected profile is warranted.

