For all other BLQ concentrations: Any other BLQ concentrations will be assigned a value of zero if they precede quantifiable samples in the initial portion of the concentration-time profile. A BLQ value that occurs between quantifiable data points, especially prior to C_{max} , will be evaluated to determine if an assigned concentration of zero makes sense, or if exclusion of the data is warranted. Following C_{max} , BLQ values embedded between 2 quantifiable data points will be treated as missing when calculating AUC. If BLQ values occur at the end of the collection interval (after the last quantifiable concentration), these will be set to zero. If consecutive BLQ concentrations are followed by quantifiable concentrations in the terminal portion of the concentration curve, these quantified values will be excluded from the PK analysis by setting them to missing, unless otherwise warranted by the concentration-time profile.

Missing Pharmacodynamic (PD) Data:

Missing 2-HG concentration data will not be imputed. Missing samples will be reported as no sample ("NS") and excluded from analysis.

Blast in Hematology and Bone Marrow Blast %:

The CRF captures hematologic blast % data in 2 fields: a numeric percentage and a text field, as some pathology reports note absent or infrequent blasts, but do not quantify the result. If the numerical blast % is missing but the text field says "absent," or inferior to 1%, 0 will be imputed for blast %. If the blast % is missing but the text field contains any of the following words: isolated, scattered, few, rare, occasional, not enumerated, no value, no total, present, less than 1%, some, then 1% blasts will be imputed. Bone marrow results of "less than 5%" will be imputed as 4.9%.

Hematology Differentials:

If the absolute values for the hematology differentials are missing but results are present in percentages, the absolute value result may be imputed as follows:

Absolute basophils = White blood cells* basophils % This approach will be taken for all hematology differential parameters.

Missing Quality of Life (QOL) Data:

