The following baseline disease characteristics will be summarized for the FAS for Phase 1 and 2, and for the EE analysis set. Baseline disease characteristics summaries will also be produced by subgroup for the following subgroups for FAS: diagnosis (AML vs. MDS) for all patients; and disease state (relapsed/refractory vs. treatment naive) for Phase 1 patients only.

- ECOG performance status at baseline
- Baseline bone marrow blasts (%): bone marrow aspirate will be used as the primary source. If no aspirate assessment is available, biopsy assessment will be used as default
- Baseline peripheral blood blasts (%)

- Categorical description of baseline values of the following laboratory parameters, as well as descriptive statistics summarizing WBC, ANC, hemoglobin, and platelets:
 - white blood cells (WBC) (< $15 \times 10^{9}/L$, 15 to < $30 \times 10^{9}/L$, $\ge 30 \times 10^{9}/L$),
 - absolute neutrophil count (ANC) (< 0.5×10^9 /L, 0.5 to < 1×10^9 /L, $\ge 1.0 \times 10^9$ /L),
 - hemoglobin (< 80 g/L, \geq 80 g/L),
 - platelet count ($<50 \times 10^9/L$, $\ge 50 \times 10^9/L$),
 - creatinine clearance (< 15 mL/min, 15 to 29 mL/min, 30 to 59 mL/min, 60 to 89 mL/min, ≥ 90 mL/min)

F. Medical and Surgical History

Medical and surgical history will be summarized on the FAS for Phase 1 and 2.

Medical histories will be coded via MedDRA version 19.1 and summarized by SOC and PT. Medical history will be summarized in a separate table from surgical history. Surgical history will be summarized by surgical category, as indicated by the investigator. Data will also be presented in a listing for the FAS.

G. Prior Anti-Cancer Therapies

Prior anti-cancer therapies will be summarized on the FAS for Phase 1 and 2, and for the EE analysis set for Phase 2. Prior anti-cancer therapy summaries will also be produced by subgroup for the following subgroup for FAS: diagnosis (AML vs. MDS).

Prior anti-cancer therapies will be summarized by ATC class and medication name, which will be coded via WHODrug (September 2016 version). Prior anti-AML/MDS therapies will also be presented in a listing for the FAS.

H. Protocol Deviations

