A swim lane plot will be created for patients in the FAS population to visualize the time on treatment with FT-2102. Time of first response and time of HSCT will be annotated on the plot. The length of the bar will represent the time (in weeks) on study, including both time on active treatment of FT-2102 and time in follow-up. The bar will be one color during active treatment, and then patients who stop treatment but are still being followed for continuing response will have the bar turn a different color. Patients who are still ongoing (either on treatment with or without response, or off treatment but being actively followed for response) will be indicated with arrows at the end of the bar. Best overall response will be annotated at the end of the bar.

A repeat of the swim lane plot will be done where there is no color coding by on/off treatment status. Rather, the bar will change color if/ when 28 days of transfusion independence is achieved. The length of the bar will represent the time (in weeks) on treatment. Best overall response will be annotated at the end of the bar.

Forest Plot

At IA2, A forest plot will be created for Phase 2 cohort 1 patients in the EE analysis set to present the CR/CRh rate compared across all of the relevant subgroups specified in the section VI.J; the subgroups not applicable to this cohort and excluded from the forest plot are diagnosis, disease state, prior IDH-1 therapy, prior FT-2102 treatment, and renal function. The plot will show the point estimate of each rate with 95% CI.

A similar plot will be created to present ORR for Phase 2 cohort 1 patients in the EE analysis set.

Hematologic Efficacy Analyses

Hematologic efficacy analyses will be performed for IA2 only.

The absolute and percent change in marrow blasts from baseline will be tabulated by visit and maximum post baseline decrease. This table summarizes blasts from either the bone marrow biopsy or bone marrow aspirate form together. At each nominal visit, if there is both a bone marrow biopsy result and a bone marrow aspirate result reported, the aspirate result will be used. Blast results of "less than 5%" will be imputed as 4.9%. No summaries will be presented when fewer than five patients' data are available at an assessment time point.

A waterfall plot will be created for Phase 2 cohort 1 patients in the EE analysis set to present the maximum % decrease in blast % experienced on study.

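### The SAP's blast imputation gives equivalent wording two different values and sets uncounted results to 1%, which can distort descriptive blast summaries

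*SAP*

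**What the plan says.** SAP VI.C, under the item on hematology and bone marrow blasts, describes the data source: "The CRF captures hematologic blast % data in 2 fields: a numeric percentage and a text field". It explains that some pathology reports mention no blasts or only sparse ones without giving a number. Three rules follow.

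- If the number is missing and the text says blasts are absent, "or inferior to 1%, 0 will be imputed for blast".
- If the number is missing and the text contains any word from a list, the value is 1%. The list starts with *isolated*, *scattered*, *few*, *rare* and *occasional*, and ends "not enumerated, no value, no total, present, less than 1%, some, then 1% blasts will be imputed".
- A bone marrow result given as under 5% "will be imputed as 4.9"%.

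The general rule at the head of VI.C is "Unless stated otherwise, missing data will not be imputed", so these rules are stated exceptions and do not conflict with it.

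Blast values are used in two places. Section VII.E summarizes baseline marrow blasts and "Baseline peripheral blood blasts" for the Full Analysis Set (FAS) in both phases and for the Efficacy Evaluable (EE) set. Section XI.B, under Hematologic Efficacy Analyses, states: "The absolute and percent change in marrow blasts from baseline will be tabulated by visit and maximum post baseline decrease". It also plans a Cohort 1 waterfall plot of "the maximum % decrease in blast % experienced on study" and mean marrow blast line plots by best response. That whole subsection is restricted to IA2.

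**The concern.** The wording has two defects.

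First, *inferior to 1%* and *less than 1%* mean the same thing but map to 0 and 1%. The value then depends on how the report was phrased and not on the patient.

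Second, the list mixes terms that describe a low count (*isolated*, *scattered*, *few*, *rare*, *occasional*) with terms that do not. *Not enumerated*, *no value* and *no total* say that no count was given. *Present* and *some* say that blasts exist but not how many. Setting these to 1% records a low figure with no information behind it.

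At stake is the accuracy of descriptive blast displays. After baseline, an unsupported 1% looks like a large fall. At baseline, it understates disease burden whenever the true count is above 1%, and it makes later percentage changes very large. A waterfall plot is sensitive to this because it keeps each patient's single largest decrease, so one imputed value can set the bar.

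**Working it through.** The plan gives no figure here to reproduce. The check sets the rules side by side and then applies them to assumed baselines.

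**Step 1: consistency of the rules (SAP VI.C, numeric field empty)**

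| Text | Information on level | Value assigned |
|---|---|---|
| *absent* | none seen | 0 |
| *inferior to 1%* | below 1% | 0 |
| *less than 1%* | below 1% | 1% |
| *isolated, scattered, few, rare, occasional* | low | 1% |
| *present, some* | exists, level unknown | 1% |
| *not enumerated, no value, no total* | none | 1% |

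Rows 2 and 3 conflict. If *inferior to 1%* is taken as a description of any result below 1%, and not as literal text, then *less than 1%* meets both rules and the SAP gives no precedence. The last two rows fall outside the stated rationale of no blasts or sparse blasts.

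**Step 2: which specimen**

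The item heading names both hematology and marrow. The sentence that introduces the two fields says hematologic blast percentage. Only the under-5% rule names bone marrow, and it is the only one of the three that XI.B repeats. Peripheral blood is therefore covered on any reading, and marrow is unsettled.

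**Step 3: size on the marrow reading**

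The documents give no patient values, so the baseline b is an assumption, taken from 5% to 90%.

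Percent change = 100 × (imputed − b) / b, with imputed = 1:

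| b (%) | Change recorded with imputed 1% | Change if the true value were 5% |
|---|---|---|
| 5 | -80.0% | 0.0% |
| 10 | -90.0% | -50.0% |
| 20 | -95.0% | -75.0% |
| 40 | -97.5% | -87.5% |
| 60 | -98.3% | -91.7% |
| 90 | -98.9% | -94.4% |

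The middle column does not depend on the true count. With b = 40% and a true on-study value of 30%, the true change is 100 × (30 − 40)/40 = -25%, and the rule would record -97.5%.

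With the imputed 1% at baseline, a later counted 5% gives 100 × (5 − 1)/1 = +400%, and a later 20% gives +1900%.

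**Step 4: size of the 0-versus-1% split**

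For the same result under 1%, the two wordings differ by 100 × (1 − 0)/b = 100/b percentage points of change. That is 20 points at b = 5% (-100% against -80%) and 1.1 points at b = 90%. In a summary of baseline levels, the split is one percentage point of blasts per affected patient.

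**Step 5: what is downstream**

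SAP XI.A takes AML and MDS response from the investigator's assessment. No section derives CR, CRh or any stopping count from the imputed blast value.

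**The case against.** The strongest reply is that the reach is narrow. The marrow change table, line plots and waterfall plot are IA2 only, so they are not planned for the final report. The word list follows a sentence about hematologic blasts, and XI.B repeats only the under-5% rule for marrow, which supports a peripheral-blood reading. On that reading every percentage in step 3 falls away. The list was also written for reports of absent or infrequent blasts, and nothing in the documents shows that a high count was ever entered as *present* or *not enumerated*.

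Most of this stands. It limits where the error can appear and leaves its frequency unknown. It does not remove the 0-versus-1% conflict, which exists for either specimen. Nor does it justify a value for *no value* or *no total*. Baseline peripheral blasts are summarized for the FAS in both phases, and that summary is not restricted to IA2.

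A reader might also infer that the rule shows false blast clearance, since 1% lies below the 5% marrow threshold in Protocol Appendix 7. The documents do not support that as a general statement. For peripheral blood the relevant criteria turn on blasts being absent: reappearance defines AML relapse in Appendix 7, and 0% is required for MDS complete remission in Appendix 8. A value of 1% keeps blasts non-zero. Text saying *absent* becomes 0, not 1%.

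**Conclusion.** The rule is wrong as written and should be corrected, but its effect is confined to descriptive output. Two statements hold without assumption: equivalent wordings receive different values, and text with no information on level receives 1%. Baseline peripheral blast summaries are exposed on any reading.

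The larger effect, a recorded change of -80% to -98.9% from one post-baseline imputed value, rests on two assumptions: that the word list applies to marrow, and that baseline lies between 5% and 90%. It would then reach baseline marrow blasts and the IA2 marrow displays.

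A reader might go further and conclude that the primary CR/CRh result or the Cohort 1 stopping decisions are inflated. The documents do not support that: response is investigator-assessed, and no test or boundary is shown to use imputed blasts. The number of affected records is not given, so the actual bias in any table or plot cannot be stated.

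**What to change.** Revise the blast paragraph in SAP VI.C as follows.

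- Keep 1% only for low-frequency terms: *isolated*, *scattered*, *few*, *rare*, *occasional*.
- Treat *not enumerated*, *no value*, *no total*, *present* and *some* as missing, unless a low-frequency term appears in the same text.
- Assign one value to every wording of under 1%.
- State whether the list applies to peripheral blood, marrow or both.
- Flag imputed blast values in the listings, as the SAP already does for imputed EQ-5D-5L data (XI.C) and derived hematology differentials (VIII.C).

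If the IA2 outputs already exist, search for affected records and correct or footnote the displays.

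A blanket ban on imputed values setting the maximum decrease in the waterfall plot is not advised. It would discard *rare* or *few* results, which remain valid at 1%, and marrow results reported as under 5%.

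The cost is one SAP paragraph, a search of the text field, and some blast values becoming missing in descriptive tables and plots. How many is not known from the documents.

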9.2.8 Quality of Life Analysis

Quality of life, as assessed by the EQ-5D-5L, will be analyzed for patients in the EE and FAS. EQ-5D-5L data will be summarized from the screening visit through cycle 4 for the FAS and EE Analysis sets (Phase 2). The number and percentage of patients reporting each score per dimension will be summarized, as well as the number reporting some problems on that dimension (score > 1). Also the change from baseline in the number reporting some problems in each dimension will be reported (raw and percent change). Additional analyses and techniques for handling missing data will be described in the SAP.

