The exploratory objectives are:

Phase 1 and Phase 2

- To assess on-target activity of FT-2102, as determined by changes in a PD biomarker in plasma
- To determine the frequency of cancer-associated mutations and/or genetic alterations in responding and nonresponding patients
- To evaluate PK/PD and clinical response relationships in each cohort

Phase 2

• To evaluate the health-related quality of life (QOL) of patients receiving FT-2102 as a single agent or in combination with azacitidine

III. Study Endpoints

A. Primary

The primary endpoints are:

Phase 1

• Incidence and severity of adverse events (AEs), clinical laboratory abnormalities, and changes in electrocardiogram (ECG) parameters

Phase 2

- All cohorts except Cohort 2: Complete Response rate (best overall response [BOR] of complete remission (CR)/complete remission with partial hematological recovery (CRh)) as determined by the investigator per disease-specific criteria. Refer to Appendix 6 for AML and Appendix 7 for MDS response criteria in the protocol.
- Cohort 2: Four-month relapse free survival (RFS) rate

B. Secondary

The secondary endpoints are:

Phase 1

- PK parameters derived from FT-2102 concentrations
- Antileukemic or antimyelodysplastic activity as determined by CR, CRh, complete remission with incomplete blood count recovery (CRi), morphologic leukemia-free state (MLFS), Marrow CR, partial remission (PR) and stable disease (SD)

Phase 2

- Evidence of clinical benefit (CRi, MLFS, Marrow CR, Overall Response (OR), Transfusion Independence (TI), Time to Response (TTR), Duration of Response (DOR), event free survival [EFS], RFS, Overall Survival (OS), and other definitions of response, including SD)
- Incidence and severity of adverse events (AEs), clinical laboratory abnormalities and changes in electrocardiogram (ECG) parameters
- PK parameters derived from plasma FT-2102 concentrations

IV. Study Design

A. Design Overview

This Phase 1/2 study will utilize a multicenter, open-label, dose-escalation design, to evaluate the safety, efficacy, PK, and PD of FT-2102 administered orally to patients with AML or MDS. Patients will be given FT-2102 daily (QD or BID) in continuous 28-day cycles, alone or in combination with azacitidine (administered at the dose of 75 mg/m² for 7 days IV/SQ per every 28-day cycle) or low-dose cytarabine (LDAC) (administered at the dose of 20 mg BID SC for 10 days every 28-day cycle) until treatment discontinuation.

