The imputation will be done according to methodology proposed by Diehr et al. (2007). Data will be imputed for missing assessments of Phase 2 patients and will be performed separately for each of five dimensions and VAS score of the EQ-5D-5L. VAS and each of the dimensions is represented by QOL in the imputation algorithm below. The five domains of EQ-5D-5L responses are ordered categories ranging from "no problems" to "extreme problems." Answers will be converted to a 5-point scale in which 1=no problems and 5= extreme problems. The VAS score of EQ-5D-5L ranges from 0 (worst health) to 100 (best health).

• Compute QOL-transformed (QOLt):

QOL score will be transformed to the probability that a person will have good QOL next cycle (have domain QOL \leq 3 next cycle; or have VAS QOL \geq 80), estimated from his QOL this cycle. All transition pairs (two values of QOL for the same person 1 cycle apart) will be used in the longitudinal data, and the transformation parameters will be estimated from a logistic regression of a binary variable "Good QOL 1 cycle later" on "QOL now." In the longitudinal data for each patient a column with one space for every cycle of that patient's potential follow-up will be created. The regression model will be as follows:

logit (Good QOL 1 cycle later) = a + b*QOL now.

The estimated probability of having good QOL 1 cycle later as a function of current QOL is then:

QOLt = Prob(Good QOL 1 cycle later | QOL) = exp(a+b*QOL)/(1+exp(a+b*QOL)).

• Compute QOL transformed with deaths added (QOLtd):

Set the values of QOLt for the cycles after a patient died to zero. For cycles after death, patients should receive a zero because they have no probability of having good QOL one cycle later.

• Compute QOLtd imputed (QOLtdi):

QOL for cycles when patients were alive but had no QOL data will be imputed from the regression of QOLtd on the logarithm of time from death (or time from the analysis date if still alive).

Calculation of time variable Cycle before death/end of follow-up (CBD):
 CBD = Cycle before death = cycle minus the integer part of (#days survived/28) + 1.

or

CBD = Cycle before end of follow-up = cycle minus the integer part of (#days on study/28) + 1

Unobserved cycles (e.g. due to missed visit, or time between last observed cycle and death when subject was alive but did not provide data) before deaths or end of followup will be imputed.

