2) Time variable CBD will be transformed to log form (LCBD) as below: LCBD=log(absolute value of CBD + 1)

- 3) A mixed model will be used to predict QOLtdi. The dependent variable is QOLtd; the mixed model will contain random intercept and slope subject effect, and fixed time effect (LCBD). QOLtdi will be predicted at imputed cycles.
- Compute QOLtdi re-transformed to the original scale (QOLback): This should be done by inverting the logistic regression equation.

QOLback = (logit(QOLt) - a)/b = [ln ((QOLt)/(1-QOLt)) - a]/b.

• Round imputed values up to the nearest whole number.

Note that no numerical values will be given after death, but "999" flags will be included to indicate cycles when patient was dead.

D. Multiple Study Centers

No stratification by the study centers will be utilized for analyses of efficacy or safety data.

E. Covariate Adjustment in Primary Analysis

Not planned for the primary analysis.

F. Sample Size Reassessment

No sample size reassessment is planned.

G. Interim Analyses

Interim analyses will be performed for the Phase 2 Cohort 1 and in other applicable Phase 2 cohorts that use two-stage designs, at defined timepoints, as outlined in section IV.C.

- Phase 2 Cohort 1: two interim analyses with 33% and 67% of patients' information respectively
- Phase 2 Cohort 2: with first 11 patients evaluable for response
- Phase 2 Cohort 6: with first 14 patients evaluable for response
- Phase 2 Cohort 7: with first 17 patients evaluable for response

• Phase 2 Cohort 8: with first 7 patients evaluable for response

As a result of these analyses, enrollment in a given cohort may be stopped early for futility, or in Cohort 1 for efficacy as well. Interim analyses that meet stopping criteria for futility are binding.

H. Multiple Comparisons

Alpha is controlled for the primary analysis within each Phase 2 cohorts. Corrections for multiple comparisons are not applied for the secondary or exploratory endpoints, as they are descriptive analyses.

I. Analysis Sets

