Line plots showing the mean (+/- SE) bone marrow blasts, ANC count, hematocrit, platelet count will be presented over time on Day 1 for cycles 1-15 for patients in the Phase 2 Cohort 1 FAS and EE analysis set by best response (CR/CRh, non-CR/CRh responders, and non-responders).

Efficacy Profiles

For IA2, For those patients who have a best overall response of PR or better, patient plots of ANC, platelet count, hemoglobin, and bone marrow blasts (analyzed as described above) will be produced for all patients in the Phase 2 Cohort 1 FAS and for patients in the Phase 1 FAS whose starting dose of FT-2102 was 150 mg BID.

C. Quality of Life Analysis

The EQ-5D-5L consists of five dimensions: mobility, self-care, usual activities, pain/ discomfort, and anxiety/depression. Each dimension has 5 levels of health state: no problems, slight problems, moderate problems, severe problems and extreme problems. The patient indicates his/her health state by selecting the most appropriate statement in each of the five dimensions. This decision results in a 1-digit number that expresses the level selected for that dimension. The digits for the five dimensions can be combined into a 5-digit number that describes the patient's health state. Present overall state of health is also to be rated on a vertical visual analogue scale (VAS) from 0 (worst health) to 100 (best health). This assessment was only performed on Phase 2 patients. EQ-5D-5L data will be summarized from the screening visit through cycle 8 for the FAS (Phase 2) and EE analysis sets (Phase 2).

Five domains of EQ-5D-5L

The number and percentage of patients reporting each score per dimension will be summarized, as well as the number reporting some problems on that dimension (score >1). Also, the change from baseline in the number reporting some problems in each dimension will be reported (raw and percent change). An additional summary table will be produced that summarizes the EQ-5D-5L data by best response (3 groups: CR/ CRh, Other Responders, Non-Responders). Missing data will be imputed as described in Section VI.C.

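### The EQ-5D-5L imputation has two separate time-axis faults: an unbracketed formula for cycles before death, and an absolute value that models post-death zeros at the same times as live scores

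*SAP*

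**What the plan says.** SAP VI.C (Missing Quality of Life Data) imputes each EQ-5D-5L dimension and the VAS separately for Phase 2 patients.

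- **Scores.** They are first transformed to the probability of good quality of life one cycle later (QOLt). The data layout is that "a column with one space for every cycle of that patient's potential follow-up will be created", so cycles after death exist as rows.
- **Deaths.** To form QOLtd, the plan says: "Set the values of QOLt for the cycles after a patient died to zero".
- **Time.** For deaths, "CBD = Cycle before death = cycle minus the integer part of (#days survived/28) + 1". For patients still alive, "CBD = Cycle before end of follow-up = cycle minus the integer part of (#days on study/28) + 1". The logged version begins "LCBD=log(absolute value of CBD + 1" and then closes its bracket.
- **Model.** QOLtd is regressed on LCBD with a random intercept and slope per patient. LCBD is the only fixed time effect.
- **Use.** Predictions are made only for cycles when the patient was alive without data. After death the output is a 999 flag.

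SAP XI.C applies this imputation to the dimension and VAS summaries, including those by best response.

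**The concern.** The model is meant to borrow from the course of quality of life as death approaches. That requires each row to carry its true distance from death, and it requires rows before and after death to be distinguishable. The formula as printed threatens the first requirement. The absolute value combined with post-death zeros defeats the second. SAP VI.C expressly imputes the gap between the last observed cycle and death, so the affected stretch is one that the method was chosen to fill. Two programmers working faithfully from the same text could also produce different imputed tables.

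**Working it through.** **Inputs.** Cycles last 28 days (SAP IV.A: "Patients will be given FT-2102 daily (QD or BID) in continuous 28-day cycles"). Write *I* for the integer part of days/28, with days counted as elapsed. Death then falls in cycle *I* + 1. Natural logs are used; the base does not affect which rows coincide. The plan states no numerical result here to reproduce.

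**Two readings of the formula**

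- Literal: CBD = cycle - *I* + 1. In the death cycle, CBD = (*I* + 1) - *I* + 1 = +2, and CBD = 0 falls at cycle *I* - 1, two cycles early. If first dose is counted as Day 1, it is one cycle early when the day count is a multiple of 28 and two otherwise.
- Bracketed: CBD = cycle - (*I* + 1). The death cycle is 0, earlier cycles are negative and later cycles positive.

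**Death on Day 100** (*I* = 3, death in Cycle 4), LCBD = log(|CBD| + 1):

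| Cycle | Row | Bracketed CBD | LCBD | Literal CBD | LCBD |
|---|---|---|---|---|---|
| 1 | alive | -3 | 1.39 | -1 | 0.69 |
| 2 | alive | -2 | 1.10 | 0 | 0 |
| 3 | alive | -1 | 0.69 | 1 | 0.69 |
| 4 | death cycle | 0 | 0 | 2 | 1.10 |
| 5 | QOLtd = 0 | 1 | 0.69 | 3 | 1.39 |
| 6 | QOLtd = 0 | 2 | 1.10 | 4 | 1.61 |
| 7 | QOLtd = 0 | 3 | 1.39 | 5 | 1.79 |

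**Fault (a), the bracket.** Literally, a living cycle *j* cycles before death has CBD = 2 - *j*. The cycle just before death (*j* = 1) therefore shares |CBD| = 1 with the cycle three before death (*j* = 3). The death cycle (*j* = 0) shares |CBD| = 2 with the cycle four before (*j* = 4). Living cycles at different distances from death are merged before any zero is involved. The end-of-follow-up formula has the same form, so survivors are affected too.

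**Fault (b), the fold.** Under the bracketed reading, *k* cycles after death gives |CBD| = *k*, and *k* cycles before death also gives *k*. The table shows Cycles 3 and 5, 2 and 6, and 1 and 7 paired, each pair being a live score and a zero. This starts once a patient survives 28 days, because then *I* is at least 1 and Cycle 1 has CBD of -1 or lower.

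**Under the literal reading the overlap is shifted.** Post-death rows have CBD of 3 or more. A living row of the same patient matches only if CBD is -3 or lower. In Cycle 1 that means 1 - *I* + 1 ≤ -3, so *I* ≥ 5, or at least 140 days of survival. Example: death on Day 150 (*I* = 5, Cycle 6) gives |CBD| of 3, 2, 1, 0, 1, 2, 3, 4 for Cycles 1 to 8, so living Cycle 1 and post-death Cycle 7 share LCBD 1.39. For shorter survival the overlap is across patients: Cycle 5 of the Day 100 death (a zero, 1.39) sits at the same time as Cycle 1 of the Day 150 death (alive, 1.39).

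**A third reading does not help.** Taking the log of |CBD + 1| still folds, around CBD = -1, where it is undefined.

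**The case against.** The strongest reply is that the sentence is prose, not code. The variable's label, and the need for an absolute value at all, suggest the bracketed meaning, under which there is no two-cycle shift. That is probably the intent, and it reduces fault (a) to an ambiguity in the text. It does not touch fault (b), which is cleanest under exactly that reading.

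A second reply is that the method follows a cited paper, that prediction is limited to living cycles and that dead cycles get only a flag. The paper was not available for this check. Limiting where the model predicts does not limit which rows it is fitted to. QOLtd is the dependent variable, and the fit is the only use the SAP states for its zeros. A programmer might sensibly leave those rows out, but the SAP does not say so.

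Three stronger inferences are tempting and should not be drawn:

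- **That the two faults chain together,** so that the shift causes zeros to mirror live scores. Under the literal reading, *k* cycles after and before death give 2 + *k* and |2 - *k*|, which are never equal for *k* ≥ 1. The shift and the exact mirror image belong to different readings.
- **That every imputed score is pulled toward poor quality of life by a known amount.** Zeros in the fit pull downward. The literal axis without zeros mixes the last cycles with earlier ones, which would pull upward if quality of life falls toward death.
- **That values after Cycle 4 are model output only.** SAP XI.C states "EQ-5D-5L data will be summarized from the screening visit through cycle 8" and protocol 9.2.8 states "EQ-5D-5L data will be summarized from the screening visit through cycle 4". However, the SAP is based on protocol version 5, and its Appendix 1 schedules EQ-5D-5L on Day 1 of Cycle 3 and beyond and at end of treatment. Scores in Cycles 5 to 8 may therefore have been observed. The difference in windows is a matter of aligning protocol versions.

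**Conclusion.** The concern stands as two separate defects. Fault (a) is conditional: it applies only if the formula is evaluated as printed, and it then misplaces time zero by two cycles (elapsed-day count). Fault (b) does not need the literal reading. It rests on the post-death zeros being in the fitted data, which the SAP's text implies and nowhere excludes. Patients alive at end of follow-up contribute no zeros, so the overlap of dead and living rows arises from deaths only.

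The documents contain no EQ-5D-5L data or missingness rates. Any simulated bias would rest on invented inputs, so neither a size nor a sign is claimed.

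The reach is limited. Quality of life is an exploratory endpoint (protocol Section 3), SAP VI.H treats such endpoints as descriptive, and imputed values are flagged in the listings. No primary endpoint or stopping rule uses them. It is still worth correcting, because the imputed summaries would otherwise depend on how one line is read and which rows are fitted.

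**What to change.** In SAP VI.C:

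1. Write CBD = cycle - (integer part of (days/28) + 1) in both formulas, and state that days are elapsed days from first dose.
2. Write the transform unambiguously as log(|CBD| + 1).
3. State that the mixed model is fitted only to cycles at or before death (CBD ≤ 0), with post-death cycles kept solely as 999 flags. On that subset the absolute value no longer merges different times.

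Separately, align the Cycle 8 window in SAP XI.C with the EQ-5D-5L schedule in force under each protocol version. Protocol 6.7 lists Day 1 of Cycles 1 to 4, with assessments stopped from Version 7/Amendment 6; SAP Appendix 1 continues beyond Cycle 3.

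The cost is one bracket in two places, one subset condition, one clarification of the window, and a re-run of the imputation and its outputs. No new data are needed.
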